6.3.1 Main Analysis

Main analyses will proceed according to the following order of procedures:

- 1) Perform single imputation for all missing pre-treatment covariates.
- 2) Estimate the probability of treatment with PrismRA for matching. Only pre-treatment covariates will be included as predictors of treatment (e.g., blinded to outcomes).
- 3) Perform stratified PS matching and describe patient characteristics of this single matched cohort. Matched external control arm should be weighted following the principle in Section 6.3 before describing patient characteristics.
- 4) Impute missing outcome data using MI as described in Section 5.4.
- 5) Within each imputed dataset, fit treatment effect outcome model with arm assignment as the independent variable with covariates adjustment.
- 6) Pool treatment effect estimates using Rubin's rule.

Steps 1-4 will be performed once at the start of analyses for each analysis population. Steps 5 and 6 will be repeated for each study endpoint and for the Treatment Policy Strategy and Composite Strategy.

Outcome regression models may also include direct adjustment for important patient covariates (e.g. age, sex, race/ethnicity, RDCI, baseline scores). In general, these methods improve confounding control in cases of imperfect matching and stratification. [30] The proportion of patients within each study arm with moderate or high disease activity at baseline who achieve an MID in CDAI of ≥ 6 (baseline moderate) or ≥ 12 (baseline high) at 24 weeks after study treatment initiation will be reported. Odds ratio and 95% CI will be estimated using weighted logistic regression.

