RA Disease Activity	
Disease activity is based on the CDAI score as follows:
 
 • Remission: CDAI \leq 2.8 • Low: CDAI $>$ 2.8 and \leq 10.0 • Moderate: CDAI $>$ 10.0 and \leq 22.0 • High: CDAI $>$ 22.0 
For the PrismRA arm, the CDAI scores will be assessed by the Investigator. The CDAI scores for the external control arm in OM1 PremiOM RA consist of CDAI scores in structured EMR data, and CDAI scores estimated by machine learning based on unstructured data.¹ CDAI scores from all data sources will be used.

5 Introduction

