8	
Patient has any active, chronic, or recurrent invasive infection (e.g., listeriosis and histoplasmosis) and/or a viral infection, that based on the Investigator's clinical assessment, makes the patient an unsuitable candidate for the study. This includes hepatitis B virus (HBV) or hepatitis C virus (HCV), recurrent or disseminated (even a single episode) herpes zoster, disseminated (even a single episode) herpes simplex, or human immunodeficiency virus (HIV).
	
Patients with the relevant diagnostic codes for chronic, or recurrent invasive infections any time prior to the study treatment initiation.
 
This includes listeriosis, histoplasmosis, coccidioidomycosis, tuberculosis, non-tuberculosis mycobacterial infections, cryptococcosis, pneumocystis pneumonia, toxoplasmosis, HBV, HCV, varicella zoster virus (VZV), herpes simplex virus (HSV), HIV.

9	
Patients with malignancy except non-melanoma skin cancer, localized prostate cancer treated with curative intent with no evidence of progression, low risk or very low risk (per standard guidelines) localized prostate cancer under surveillance/watchful waiting (without intent to treat), or carcinoma in situ of any type (complete resected).
	
Patients with cancer diagnostic codes any time prior to the study treatment initiation will be excluded. This includes all malignancies except non-melanoma skin cancer.
 
Allowing for localized and cured cancers is not replicable in real-world data and will not be attempted.

10	
Patients who are unable to understand the protocol and unable to provide informed consent.
	
This criterion is not replicable in real-world data and will not be used.

11	
Patients who are not indicated for PrismRA.
	
This criterion is not replicable in real-world data and will not be used.
 
The assumption will be made that the careful replication of the above inclusion and exclusion criteria will ensure a comparable indication for PrismRA in the external control arm.

12	
This point does not apply to the PrismRA arm.
	
Patients will be excluded if they have been cared for by rheumatologists who have participated in the PrismRA arm any time in the past to avoid including patients using PrismRA.

8 Study Procedures

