10.4 Planned Outcome Analysis

The previously stated outcome measures will be compared across the PrismRA arm and the external control arm after propensity score modelling. For all outcome measures, point estimates as well as two-sided 95% confidence intervals (CIs) will be provided. Hypothesis testing will be

two-sided with an alpha level of 5%. For proportion outcome measures, Pearson's χ^2 test will be utilized. For continuous outcome measures, unpaired t-test will be used.

Refer to the study's SAP for additional details.

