5.2 Analysis Populations

PrismRA arm:

This arm will enroll approximately 600 RA patients at approximately 33 clinical sites who are at least 18 years of age. All patients in the PrismRA arm will undergo PrismRA testing at their first study visit (Visit 1). See Section 6.1.1 and 6.1.2 for patient inclusion and exclusion criteria for details.

This study will perform analyses for two sets of populations from the PrismRA arm. The first one is the modified ITT analysis population, which consists of patients that initiate the study

treatment at Visit 2. A sub-population of patients who are adherent to the PrismRA test results will also be analyzed. This sub-population will exclude patients who initiated TNFis despite having a PrismRA result indicating a molecular signature of non-response to TNFi therapies.

External control arm:

Patients with RA in the OM1 PremiOM RA Dataset will be selected based on the same eligibility criteria as in the PrismRA arm and adapted for real-world data availability where necessary. Patients in the external control arm will be balanced with patients in the PrismRA arm using a propensity score (PS) model developed with the primary goal of achieving balance in baseline characteristics between the comparison groups. The external control arm is expected to have at least 1,500 eligible patients, with no less than 750 patients having CDAI scores at both baseline and Week 24. Data from patients who initiated b/tsDMARDs in the contemporaneous period (March 2022 and onward) will be used and if needed, the recent historical period (6-month to 3-year period prior to March 2022) will be used to maximize the size of the patient pool while minimizing confounding by the potential secular trends in treatment patterns. The PS model building process will aim to retain the inclusion of as many PrismRA arm participants as possible. If less than 95% of the PrismRA arm is included due to the lack of a matched control or non-overlapping PS, the historical period will be used for identifying external control patients. The smallest historical time window that can retain inclusion of greater than 95% of PS matched PrismRA patients will be used. The overlap in PS distributions between the external control and PrismRA arms will inform the ultimate sample size.

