6.1.2 Exclusion Criteria

Table 3. describes the exclusion criteria that will be used prospectively in the PrismRA arm and their best approximation for the selection of comparable patients in the observational external control arm.

In addition to the exclusion criteria outlined below, this study will exclude patients in the external control arm that are managed by physicians participating in the PrismRA arm to avoid potential for contamination bias (e.g., erroneous inclusion of patients who received PrismRA). Patients whose study treatment initiation is managed by PrismRA physicians identified by National Provider Identifier (NPI) will be excluded from eligibility.

Table 3. Exclusion criteria by study arm

PrismRA arm	External control arm

1	Patient has any non-study limitation precluding patient receipt of the PrismRA test (e.g., financial, or logistical limitations).	It assumes patients who used b/tsDMARDs did not have such limitations that would have prevented the potential receipt of the PrismRA test had it been offered.
2	Concurrent treatment with an investigational product or use of an investigational product less than 4 weeks prior to Visit 1.	This criterion is not replicable with real world dispensing data and will not be used.
3	Patient cannot have participated in an observational study at least 4 weeks prior to Visit 1.	This criterion is not replicable in real-world data and will not be used.
4	The use of RA therapies outside of FDA-approved indication.	This criterion is not replicable with real-world dispensing data and will not be used.
5	Patient has been previously exposed to any non-TNFi b/tsDMARDs (FDA approved or experimental).	
Patients who have been previously exposed to any non-TNFi b/tsDMARDs any time during their history prior to the study treatment initiation will be excluded.
 
The list of non-TNFi b/tsDMARDs approved for RA includes the following:
 
IL-6i (tocilizumab, sarilumab)
 
IL-1i (anakinra)
 
T-cell co-stimulation inhibitor (abatacept)
 
B-cell depletion agent (rituximab)
 
JAKi (tofacitinib, baricitinib, upadacitinib)
 
The list of non-TNFi b/tsDMARDs not currently approved for RA includes the following:

		IL-23i (guselkumab, risankizumab, tildrakizumab, ustekinumab [IL-12/IL-23i]) IL-17i (secukinumab, ixekizumab, brodalumab)

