6.3.2 Sensitivity Analysis

Sensitivity analyses will assess the robustness of treatment effect estimates to limiting primary endpoint to patients who have the complete CDAI scores.

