6.4.1 Secondary Analysis

Statistical approaches for secondary study endpoints follow all methods described in Section 6.3.

For binary endpoints, the proportion of patients within each study arm meeting the outcome of interest will be calculated. Odds ratio and 95% CI will be estimated using weighted logistic regression.

For the continuous endpoint (change in CDAI scores), the average change in CDAI scores along with the average difference and 95% CI estimated using weighted least squares will be reported.

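### Physician is nested in arm, yet no planned interval names a variance for site or physician correlation, and the 88% power assumes independent patients; the effect depends on an ICC the plan does not give

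*SAP*

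**What the plan says.** **Who can be in which arm.** SAP 6.1.2: "Patients whose study treatment initiation is managed by PrismRA physicians identified by National Provider Identifier (NPI) will be excluded from eligibility". Protocol 7.4.2, row 12, is to the same effect: "Patients will be excluded if they have been cared for by rheumatologists who have participated in the PrismRA arm any time in the past". On the source of PrismRA patients, SAP 5.2 says: "This arm will enroll approximately 600 RA patients at approximately 33 clinical sites". On scoring, Protocol section 4 says: "For the PrismRA arm, the CDAI scores will be assessed by the Investigator".

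**How the intervals are formed.** For the primary endpoint SAP 6.3.1 says "Odds ratio and 95% CI will be estimated using weighted logistic regression", with Rubin pooling over the imputed datasets. For change in CDAI, SAP 6.4.1 says "average difference and 95% CI estimated using weighted least squares will be reported". The sensitivity analysis in SAP 6.3.2 checks robustness to "limiting primary endpoint to patients who have the complete CDAI scores", and 6.4.2 repeats this. Protocol 10.4 gives Pearson's chi-square for proportions and adds "For continuous outcome measures, unpaired t-test will be used", then refers to the SAP for detail.

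**What is not named.** None of these sections mentions a robust or sandwich variance, a random effect or a clustering unit. Neither site nor physician is a covariate in SAP Table 4; geography is the nearest item. GEE appears in the SAP's abbreviation list and in two reference titles, but in no analysis section.

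**Power.** SAP 5.1 and Protocol 10.1 obtain 88% from Fisher's exact test of two independent proportions, with no design effect.

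**The concern.** No physician contributes patients to both arms, so differences between physicians do not cancel in the comparison. Patients of one site or physician may share prescribing habits, follow-up practice and an unblinded CDAI assessor. SAP 5.5 itself recognises, for retrospective data, that response criteria and documentation differ between and within sites. If outcomes correlate within site or physician, a model-based standard error that treats patients as independent is too small, and power computed for independent patients is too high.

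At stake are the width of the interval for the primary odds ratio, the reliability of the complete-case check on it, and the power figure that supports the sample size.

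**Working it through.** **1. Inputs from the documents.** 600 and 1,500 patients before attrition; attrition 45% and 50%; response 40% versus 30%; two-sided alpha 0.05; about 33 PrismRA sites; matched controls about twice the PrismRA arm (SAP 6.3).

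- Observed for power: 600 × 0.55 = 330 and 1,500 × 0.50 = 750.
- Observed per site: 330 / 33 = 10.
- Matched complete cases: 330 versus 2 × 600 × 0.50 = 600.

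**Assumptions.** ICC from 0.01 to 0.05, and cluster sizes other than 10. The documents give no ICC, no number of physicians per site and no control cluster size.

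**2. The plan's own figure.** SE = √(0.40×0.60/330 + 0.30×0.70/750) = √(0.000727 + 0.000280) = 0.03174. Power = Φ(0.10/0.03174 − 1.96) = Φ(1.19) = 88.3%. Exact power of Fisher's test is 88.4%. The stated 88% is correct for independent patients.

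**3. Same basis, PrismRA arm clustered.** Multiply the first variance term by DEFF = 1 + (m − 1) × ICC. For m = 10 and ICC 0.05, DEFF = 1.45, SE = √(0.001055 + 0.000280) = 0.03653 and power = Φ(0.777) = 78.2%.

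| Observed per cluster | ICC 0.01 | ICC 0.02 | ICC 0.05 |
|---|---|---|---|
| 10 (a whole site) | 86.3% | 84.2% | 78.2% |
| 5 | 87.4% | 86.5% | 83.8% |
| 3 | 87.9% | 87.4% | 86.1% |

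If controls also cluster in tens, the first row becomes 85.5 / 82.7 / 74.4%.

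**4. Planned multiple-imputation (MI) analysis, type I error without a clustered variance.** This was simulated: 33 sites × 18 = 594 PrismRA patients (10 observed per site) and 1,200 controls (600 observed). Data were missing completely at random. Normal scores were imputed within arm without site, dichotomised after imputation, and the log odds ratio was pooled by Rubin's rule. Ranges cover separate runs, with and without a 12-week score.

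| Clusters | ICC 0 | 0.01 | 0.02 | 0.05 |
|---|---|---|---|---|
| Whole site, equal sizes | 2.9–3.1% | 3.5–4.0% | 4.3–4.7% | mostly 6.4–7.2% (one short run 5.9%) |
| Physician, 5 observed | | | | 4.5–5.0% |
| Physician, 3 observed | | | | 3.7% |

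At ICC 0.05 with site clusters the mean reported SE was 0.1454 against an empirical SD of 0.1573 (0.1392 against 0.1500 with a 12-week score), so 7–8% too small. Unequal sites (6 to 44 patients) gave 8.2%, and controls clustered at 5 observed per physician gave 8.0%.

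**5. Complete-case analysis, 330 versus 600.** Type I error = 2Φ(−1.96 × √[(1/330 + 1/600)/(DEFF/330 + 1/600)]). At ICC 0.01 (DEFF 1.09) the ratio is 0.004697/0.004970 and the error 5.7%. At ICC 0.05 (DEFF 1.45) it is 0.004697/0.006061 and the error 8.4%. Simulation gave 5.4% and 7.6–8.5% with equal sites, and 5.7% and 10.5% with unequal sites.

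**6. With a cluster-robust variance and t(32) reference.** Type I error was 2.7–5.3% for MI across runs and 4.2–4.9% for complete cases. MI power without / with a 12-week score was 88.5 / 91.2% at ICC 0.01, 85.7 / 89.9% at 0.02 and 82.3 / 84.0% at 0.05 with site clusters. With 5 observed per physician it was 89–91% throughout.

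The simulations omit covariate adjustment, the matching weights and the no-switch component of the composite endpoint.

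**The case against.** The case against is substantial, and much of it stands.

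- **A reader might infer that 88% is wrong, or fails for the planned analysis at any positive ICC.** Neither follows. The figure is right for its stated test. It is an observed-case figure, whereas the primary analysis is MI, whose simulated power at ICC 0 is 90.6% (92.4% with a 12-week score). With robust variance it is still about 88% or more at ICC 0.01.
- **A reader might take a design-effect error rate for 330 versus 750 as the error of the primary test.** No planned test has those numbers: the main analysis is MI after matching, and the complete-case analysis has about 330 versus 600.
- **The nesting is shown for physicians, not sites.** The SAP excludes by NPI, so a non-participating physician at a participating site is not clearly excluded. With physician-sized clusters and independent controls the MI test stays at or below 5%. This limits the harm but does not remove the point: correlation within site needs no perfect nesting by site.
- **Correlation may be small.** The endpoint is change from baseline, so a constant scoring offset largely cancels, apart from the moderate/high classification. Covariate adjustment and matching on geography may lower it further. This is plausible, but the documents do not argue it.
- **The complete-case analysis carries no decision rule.** True, but it is the only sensitivity analysis the SAP commits to, and its interval will be read as support for the primary result.
- **Protocol 10.4 adds little,** since it defers to the SAP. Agreed.

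The word weighted does not answer the concern: SAP 6.3 defines matching weights, not a variance estimator.

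**Conclusion.** The concern holds in conditional form. Physician is nested in arm, no planned interval allows for site or physician correlation, and 88% rests on an unstated assumption of independent patients.

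- **Power, observed-case basis:** about 86 / 84 / 78% at assumed ICC 0.01 / 0.02 / 0.05 with 10 observed per site and independent controls; 84–88% with 3–5 per cluster.
- **Main MI test:** within 5% up to ICC 0.02 and with physician-sized clusters; about 6.5–7% at ICC 0.05 if a whole site is one cluster, and higher if sites are unequal or controls also cluster.
- **Complete-case analysis:** about 5.4–6% at ICC 0.01 and 8% at 0.05 with equal, site-sized clusters. It lacks the conservatism that imputing and then dichotomising gave the MI test in simulation.

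The excess error lies in both tails, so a reader should not infer a bias towards PrismRA from clustering alone. Every adverse figure rests on an assumed ICC and cluster size. The MI protection at low ICC was found in a simplified simulation; the plan does not claim it.

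**What to change.** 1. **SAP 6.3.1 step 5, 6.3.2, 6.4.1 and 6.4.2.** Specify a cluster-robust (sandwich or GEE) variance for the weighted logistic and weighted least-squares models. Apply it within each imputed dataset before Rubin pooling, and in the complete-case analyses. Cluster on site in the PrismRA arm and on treating provider in the control arm where a provider key is kept; otherwise treat each control as its own cluster and state that limit. Use a small-sample correction and a t reference suited to about 33 clusters.
2. **SAP 5.1 and Protocol 10.1.** State that 88% assumes independent patients, and show power over an assumed ICC range such as 0.01–0.05.
3. **Report.** Say that this corrects the variance only and does not remove confounding of arm with physician or site.

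**Cost.** Mainly wording, slightly wider intervals and a less favourable stated power. If the ICC is zero, allow 1 to 2 points of power; in the MI simulation it fell from 90.6 to 89.5%, or from 92.4 to 91.5% with a 12-week score. PrismRA site is already held, since Protocol 14.2 reviews deviations by site, but it must reach the analysis file. A control provider key may need a change to the dataset specification, because Protocol 12.4.1 limits the elements kept; the fallback avoids this.

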6.3.2 Sensitivity Analysis

Sensitivity analyses will assess the robustness of treatment effect estimates to limiting primary endpoint to patients who have the complete CDAI scores.

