5.0 GENERAL STATISTICAL CONSIDERATIONS

5.1 Sample Size and Power Calculations

The study is powered to detect a difference of 10% in the proportion of patients with improvement in CDAI from baseline to Week 24 by at least the MID as defined in Section 3.1 between the PrismRA arm and the external control arm. Results are shown in **Table 1**. It is estimated that the attrition rate at Week 24 (defined as the proportion of patients with missing CDAI scores at Week 24 for any reason) can be up to 45% in the PrismRA arm and up to 50% in the external control arm. The sample sizes below have been inflated accordingly to account for the patient attrition mentioned above.

With a sample size of 600 in the PrismRA arm and 1,500 in the external control arm, the study has 88% power to establish the superiority of the PrismRA intervention as compared to the standard of care by detecting a difference of 10% between the two study arms based on Fisher’s

exact test of independent proportions assuming the proportion of patients with improvement in CDAI by MID are 40% and 30% in the PrismRA arm and the external control arm, respectively.

Table 1. Study power for comparing proportion of patients with improvement in CDAI from baseline by at least MID between the two study arms

Sample size in the PrismRA arm before attrition	Sample size in the external control arm before attrition	Proportion of patients in the PrismRA arm with MID improvement in CDAI	Proportion of patients in the external control arm with MID improvement in CDAI	PrismRA arm, attrition			
				30%	35%	40%	45%
				Study power			
600	1,000	0.45	0.35	86%	84%	82%	80%
600	1,000	0.40	0.30	87%	86%	84%	82%
600	1,000	0.35	0.25	90%	89%	87%	85%
600	1,500	0.45	0.35	91%	90%	88%	86%
600	1,500	0.40	0.30	92%	91%	89%	88%
600	1,500	0.35	0.25	94%	93%	92%	90%
600	2,000	0.45	0.35	93%	92%	90%	88%
600	2,000	0.40	0.30	95%	93%	92%	90%
600	2,000	0.35	0.25	96%	95%	94%	92%

The sample size calculation was performed with SAS (version 9.4, Cary, NC).

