5.3 Data Summarization and Analysis

Summary statistics for continuous variables to be reported will include mean, median, standard deviation (SD), 25th and 75th percentile. Categorical variables will be reported using counts and proportions. Hypothesis testing will be two-sided with an alpha level of 5%. For all outcome measures, point estimates as well as two-sided 95% confidence intervals (CIs) will be provided. P-values will be reported where appropriate to four decimal points unless all p-values in a table are greater than 0.01 in which case p-values will be reported to three decimal points in that table as the fourth decimal point is not needed. Details of the specific analytic methods are described below (Section 6).

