5.4 Handling Missing Data

Missing data will be handled with two approaches: (1) minimizing the chance of missing data in the study design and conduct stages, and (2) handling missing data with statistical methods in the analysis phase.

The following measures will be taken to reduce missing data in the study design.

PrismRA arm: Missing data will be minimized through rigorous conduct of data collection as described in Section 8.9 of the Protocol. See below for the handling of missing follow-up data.

External control arm: At least one observed CDAI measurement in the 3-month period prior to the index date (b/tsDMARD initiation) and at least three observed CDAI measurements in the 12-month period prior to the index date (including the measurements in the aforementioned 3-month period) will be required to ensure patients are selected from practices where CDAI are recorded as a part of routine care.

The following statistical methods will be considered in handling missing data in the analyses.

The rigorous design of the study aims to reduce the amount of missing data in baseline variables. If needed, single imputation [8] of missing baseline characteristics will be used to ensure that all eligible patients are included in the PS model to estimate the probability of treatment [9] for confounding control. Further details of the treatment PS methods are described below in Section 6.3.

Longitudinal outcomes may be unobserved due to patients that are lost-to-follow up ("drop-out"), missed scheduled visits (PrismRA arm), encounters that fall outside of the specified follow up window (external control arm) or not measured during a completed visit. It is anticipated that at 24-weeks roughly 45% of the PrismRA arm and 50% of the external control arm will be missing outcome data. Within each study arm the number and proportion of missing outcomes at

12 and 24-week visits will be described and baseline characteristics of patients with complete versus incomplete outcome data will be compared.

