8.0 CONSIDERATIONS FOR FUTURE ANALYSES

MI for missing data is performed under the assumption that data are MAR. This assumption is sensitive to (1) differential rate of discontinuation between study arms that is also related to prognostic factors (e.g., informative drop-out) and (2) the possibility of unmeasured confounders. To assess the robustness of the MAR assumption sensitivity analyses may be performed. To analyze the sensitivity of treatment effect estimates to informative drop-out, missing outcomes are first imputed for completed visits and missed or out-of-window visits that occur prior to study drop-out. Any remaining missing outcomes occurring due to drop-out will

be accounted for using inverse probability of censoring weights (IPCW). [33-35] The IPCW method is a regression approach that assigns weights to each individual based on the inverse of the estimated probability of having complete follow-up data. A logistic regression model is used to predict the probability of having missing outcome data conditional on baseline and time-varying covariates at available follow-up visits. The IPCW are subsequently applied to individuals with complete (observed and imputed) data in outcome models creating a pseudo-population such that the inference is with respect to the original full cohort. [31] For outcome models using inverse probability of treatment weights (IPTW) and IPCW methods simultaneously, the individual weights are multiplied, and the resulting weighted treatment effect estimate is referred to as an inverse-probability-of-treatment-and-censoring weighted estimate (IPTCW). [25] To assess robustness of the modeling assumptions to different missing data mechanisms (e.g., not MAR), a “tipping-point” analysis [36] may be conducted that test a series of pre-determined alternative assumptions for reasons outcome data are missing during follow-up.

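### The only committed sensitivity analysis for missing Week 24 outcomes is complete-case, which cannot show how the result depends on missingness tied to the unobserved outcome

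*SAP*

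**What the plan says.** SAP 5.4 states: "It is anticipated that at 24-weeks roughly 45% of the PrismRA arm and 50% of the external control arm will be missing outcome data". SAP 5.1 uses the same percentages as ceilings in the power calculation, saying that attrition "can be up to 45% in the PrismRA arm and up to 50% in the external control arm". For the primary analysis, SAP 5.4 applies multiple imputation (MI) under MAR, separately by arm, using baseline, Week 12 and Week 24 data. It imputes continuous scores and then derives the binary endpoints from them.

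SAP 6.3.2 contains one sentence: "Sensitivity analyses will assess the robustness of treatment effect estimates to limiting primary endpoint to patients who have the complete CDAI scores". SAP 6.4.2 repeats it almost word for word, and Table 4 is the only sensitivity table shell. Protocol 10.5 promises a sensitivity analysis for robustness and leaves the details to the SAP.

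SAP 8.0, which deals with considerations for future analyses, acknowledges that MAR is vulnerable to differential, informative dropout. It then says: "To assess the robustness of the MAR assumption sensitivity analyses may be performed". It describes inverse probability of censoring weighting (IPCW) and a tipping-point analysis in the same permissive terms, and gives no shift sizes, range or trigger for either.

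SAP 5.4 also commits to reporting missingness by arm and comparing the baseline characteristics of patients with and without outcome data.

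**The concern.** Nearly half of the primary outcomes may come from the imputation model, so the result depends on what is assumed about patients who were not seen at Week 24. A complete-case analysis uses only observed outcomes. If patients who are doing worse at Week 24 are less likely to be measured, beyond what Week 12 and baseline data predict, MI and complete-case can be biased the same way and still agree. The baseline comparison in SAP 5.4 cannot detect this, and the Treatment Policy analysis changes the handling of switches rather than the missing-data assumption.

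The two arms also lose outcomes by different routes. SAP 5.4 lists missed scheduled visits for PrismRA and encounters outside the follow-up window for controls. The Protocol 8.6 windows are ±2 weeks for PrismRA and ±4 weeks for controls. Nothing in the design makes departures from MAR cancel between arms. The comparison is open-label and non-randomised, and if the relevant sensitivity analysis stays optional, the decision to run it can be made after the result is known.

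**Working it through.** **Inputs.** SAP 5.1: 600 and 1,500 patients before attrition; 45% and 50% attrition; response 40% vs 30%; Fisher's exact test. SAP 5.3: two-sided alpha of 5%.

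**Plan's own figure.** Observed patients: 600 × 0.55 = 330 and 1,500 × 0.50 = 750. Exact power of the two-sided Fisher test at 40% vs 30% is 88.4%, against the stated 88%. The power calculation reproduces and is not at issue.

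**Amount missing.** 600 × 0.45 = 270 and 1,500 × 0.50 = 750, so 1,020 of 2,100, or 49%.

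**Margin over significance.** SE = √(0.40 × 0.60/330 + 0.30 × 0.70/750) = 0.0317. Then 1.96 × SE = 6.2 points, and the lower 95% limit is 10 − 6.2 = 3.8 points.

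**Departures from MAR** (SE held fixed; d is the gap between the true and the imputed response rate among missing patients):

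| Scenario | Change in difference | Significance lost at | Difference is zero at |
|---|---|---|---|
| PrismRA missing lower, controls as imputed | −0.45d | 3.78/0.45 = 8.4 points (31.6% instead of 40%) | 10/0.45 = 22.2 points |
| Opposite directions, same size | −0.95d | 3.78/0.95 = 4.0 points | 10/0.95 = 10.5 points |
| Both arms lower by the same amount | +0.05d | not lost | not reached |

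For the last row, take d = 10: 40 − 4.5 = 35.5% and 30 − 5 = 25.0%, a difference of 10.5 points. In every row the observed data are unchanged, so the complete-case difference stays at 10 points.

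**Fewer controls.** SAP 6.3 targets about twice as many matched controls as PrismRA patients. That is 1,200, or 600 observed after 50% attrition. SE = √(0.24/330 + 0.21/600) = 0.0328, 1.96 × SE = 6.4 points, and the PrismRA-only value is (10 − 6.43)/0.45 = 7.9 points.

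**Smaller imputed share.** Under the Composite Strategy (SAP 3.0, 3.1) a known switcher is a failure whatever the CDAI, so the share depending on imputation may be below 45%. The documents give no switch rate. With the same SE and an assumed PrismRA share of 35%, the value is 3.78/0.35 = 10.8 points; at 30% it is 3.78/0.30 = 12.6 points.

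**The case against.** The imputation model includes Week 12 data, so dropout that follows observed early response is within MAR. The covariates named for the outcome model in SAP 6.3.1 are baseline ones, so complete-case and MI can diverge when dropout follows Week 12 response, and comparing them is informative about that mechanism. This stands. It would be wrong to say that complete-case tells us nothing about response-related dropout.

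Nor is complete-case always the stronger assumption. An odds ratio from observed patients stays consistent under some outcome-dependent mechanisms, for example when missingness depends on outcome by the same factor in both arms. This also stands, but it gives no protection when the dependence differs by arm.

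The magnitude rests on unfavourable directions, an unadjusted risk difference and the full 45% share. It ignores imputation, matching and weighting variance, whereas the SAP will report a weighted odds ratio. That is fair: the figures are illustrative, and the documents give neither the size nor the direction of any departure.

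A reader might infer that the plan would present a fragile result as robust. The documents do not support that. No section commits to a robustness claim, and SAP 8.0 states the weakness of MAR openly. A reader might also take IPCW as a test of MAR, but as SAP 8.0 describes it, it models missingness from measured covariates and so shares the limitation. No method can test MAR from the observed data; a tipping-point analysis shows how far the conclusion depends on it.

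**Conclusion.** The gap is real and should be closed. With 45% to 50% of Week 24 outcomes expected to be missing, the SAP commits to no analysis that shows how the primary result depends on missingness related to the unobserved outcome. The one suitable method it names is left optional and unspecified.

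At the planning rates, a PrismRA-only departure of about 8.4 points, or opposite departures of about 4 points, would remove significance. Equal same-direction departures would not, so only a difference between arms matters. If known switchers reduce the PrismRA share that depends on imputation to an assumed 35% or 30%, the PrismRA-only value becomes about 10.8 or 12.6 points. Confidence is high on what the SAP does and does not commit to. It is lower on the size of the consequence, which rests on the simplifications in the working.

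**What to change.** Move the tipping-point analysis from SAP 8.0 into 6.3.2 as a required analysis of the primary endpoint:

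- After the MAR imputation, add arm-specific shifts, fixed in advance, to the imputed Week 24 CDAI scores over a two-way grid: worse in PrismRA, better in control, with equal shifts in both arms included. The shifts belong on CDAI because SAP 5.4 derives the binary endpoint from the imputed scores.
- Re-derive the MID endpoint, keeping known switchers as failures under the Composite Strategy.
- Rerun steps 5 and 6 of SAP 6.3.1. Matching comes before outcome imputation in that sequence, so the matched cohort does not change.
- Report the shifts, and the implied response rates among imputed patients, at which the 95% CI first includes no effect.
- Keep complete-case as supportive.

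The cost is a revision of the SAP text, a further table shell and modest programming on imputed datasets that the plan already produces. No new data are needed. The other consequence is that a fragile result may be shown to be fragile.
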